### 13.5 Analysis of Primary Endpoint

The primary endpoint is bi-compartmental PFS defined as time from first dose of atezolizumab (day 1 cycle 1) to progression or death due to any cause. Progression is defined as the first detection of radiologic progression of intracranial (per RANO-BM criteria; Section 11.1), extracranial (per RECIST 1.1 criteria; Section 11.2), or both or unequivocal progression of non-measurable disease in the opinion of the treating physician (an explanation must be provided). The PFS will be analyzed using Kaplan–Meier product-limit estimates and will be plotted with two-sided 90% confidence bands using Greenwood’s formula for the variance. For evaluating median survival, a Brookmeyer-Crowley like test will be conducted using the one-sided  $\alpha = 0.05$ .

## 13.6 Analysis of Key Secondary Endpoints

### 13.6.1 Extracranial Objective Response:

The design of this study, which involves radiation to CNS metastases in the setting of evaluable extracranial disease, provides a unique opportunity to test whether there is a signal consistent with an abscopal effect with the addition of stereotactic radiation to atezolizumab. Extracranial response will be assessed according to RECIST 1.1, and will be evaluated as a key secondary objective using a one-sample exact binomial test (one-sided type I error  $\leq 0.05$ ).

In prior studies evaluating immune checkpoint inhibitors in metastatic triple negative breast cancer (which excluded patients with active CNS metastases), the extracranial response rate has ranged from 8.6% in an unselected population [Dirix *et al.*, 2015] (Dirix *et al.*, 2015), to 18-19% in patients selected for tumor PD-L1 expression [Emens *et al.*, 2015, Nanda *et al.*, 2016]. Based on these prior studies of single agent PD1/PDL1 blockade in unselected triple negative breast cancer, the null hypothesis is that the extra-CNS response rate is 10% or lower.

With a sample size of 45 defined by the primary endpoint of PFS, there will be 82% power to reject the null hypothesis if the true extra-CNS response rate is 25% with stereotactic radiation given in combination with atezolizumab.

The observed extra-CNS response rate will be reported with a two-sided 90% confidence level which given the sample size will have a maximum width of 26%. In addition, we intend to evaluate extracranial objective according abscopal response as by Golden *et al.* [Golden *et al.*, 2015].

### 13.6.2 Overall survival

Overall survival is defined as the time from first dose of atezolizumab (day 1 cycle 1) to death from any cause. Patients who are alive at the end of the study will be censored at the date of last known alive. OS will be analyzed using Kaplan–Meier product-limit estimates and will be plotted with two-sided 90% confidence bands using Greenwood’s formula for the variance. For evaluating median survival, a Brookmeyer-Crowley like test will be conducted using the one-sided  $\alpha = 0.05$ . Based on prior studies [Eichler *et al.*, 2008, Lin *et al.*, 2008, Nam *et al.*, 2008, Niwinska *et al.*, 2010, Anders *et al.*, 2011], the null hypothesis is that median overall survival is 5 months or less.

With a sample size of 45 defined by the primary endpoint of PFS, there will be 90% power to reject the null hypothesis if the true median OS is 10 months when patients are given stereotactic radiation in combination with atezolizumab. The Approximate Upper Critical Value to the hypothesis test is a median OS of 7.4 months, under the assumption of nonparametric exponential family of density function for the distribution of failure times. The following table shows the level of power if smaller levels of improvement in survival are true which may be clinically relevant.

Alternative Hypothesis: Median OS (HR versus null)	Power
10 months (HR = 0.5)	90%
8.33 months (HR = 0.6)	75%
8 months (HR = 0.625)	70%
7.5 months (HR = 0.667)	61%

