### **5.7 Criteria for Taking a Participant Off Study**

Participants will be removed from study when any of the following criteria apply:

- Lost to follow-up
- Withdrawal of consent for data submission
- Death
- Study closure

The reason for taking a participant off study, and the date the participant was removed, must be documented in the case report form (CRF) and CTMS (OnCore).

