### 13.2 Sample Size, Accrual Rate and Study Duration

The primary endpoint is bi-compartmental PFS according to RANO-BM criteria. A sample size of 45 was chosen to achieve 80 % power to detect a difference between the null hypothesis median PFS of 2 months and alternative of 3.5 months at a one-sided type I error of 0.05.

The null hypothesis was derived from two sources: First, a prospective trial testing the combination of irinotecan and iniparib in patients with metastatic triple-negative breast cancer and new/progressive brain metastases reported a median time to progression (which included both intracranial and extracranial progression) of 2.14 months [Anders *et al.*, 2014]. Next, in a retrospective study describing outcomes of breast cancer patients after initial stereotactic radiation, time to intracranial progression was significantly shorter in patients with triple-negative breast cancer, relative to the luminal A subtype (HR 28.0 in multivariable model,  $p=0.003$  [Dyer *et al.*, 2012]. Although the numbers are small, the point estimate for the time to intracranial progression in the triple-negative subset was 2.5 months [Dyer *et al.*, 2012].

Anticipated accrual of approximately 2 patients per month, it will require approximately 24 months of patient accession to reach 45 patients. The primary analysis of PFS and OS will be

time-driven and performed after 6 months of additional follow-up.

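### Section 13.6.2: at the stated N=45, the 7.4-month OS critical value and the power table beside it (61% at a true median of 7.5 months) cannot both be right

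*Combined protocol and SAP*

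**What the plan says.** Section 13.6.2 sets the null: "the null hypothesis is that median overall survival is 5 months or less". The method, at an alpha of 0.05, is given as follows: "For evaluating median survival, a Brookmeyer-Crowley like test will be conducted using the one-sided". OS is estimated by Kaplan-Meier and "plotted with two-sided 90% confidence bands using Greenwood’s formula for the variance". Greenwood is thus named for the bands. No scale or variance is named for the test, and no rejection rule is given as a patient count.

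With 45 patients, a number taken over from the PFS design, the section claims 90% power at a median of 10 months. It then gives the critical value: "The Approximate Upper Critical Value to the hypothesis test is a median OS of 7.4 months". The distributional basis for that value is described in these terms: "under the assumption of nonparametric exponential family of density function for the distribution of failure times". The table that follows prints 90% at 10 months, 75% at 8.33, 70% at 8, and 61% in the row "7.5 months (HR = 0.667").

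Section 13.2 says the analysis is "time-driven and performed after 6 months of additional follow-up", once accrual of about 2 patients a month over about 24 months has ended.

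**The concern.** A true median of 7.5 months lies just above a critical value of 7.4 months. An estimate centred near 7.5 should exceed 7.4 only slightly more than half the time, so power there should be close to 50%. The plan prints 61%.

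OS is a key secondary endpoint with its own formal one-sided test. If the threshold and the power come from different calculations, a reader cannot tell which rule will be applied or what power it has.

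**Working it through.** **Inputs.** N = 45, null median 5 months, one-sided 0.05 and exponential OS (Section 13.6.2); at least 6 months' follow-up for every patient at analysis (Section 13.2).

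**Reduction to a count.** Follow-up exceeds 5 months for everyone. Without earlier loss to follow-up, a Brookmeyer-Crowley-type test of the 5-month null depends only on X, the number of 45 alive at 5 months. For true median m, X is binomial with p = 0.5^(5/m): 0.500, 0.630, 0.648, 0.660 and 0.707 at m = 5, 7.5, 8, 8.33 and 10.

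**Reproducing the table.** Exact binomial tails, with the exponential-equivalent median 5 × ln 2 / (−ln(k/45)):

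| Rule | Equivalent median | Exact size | 7.5 | 8 | 8.33 | 10 |
|---|---|---|---|---|---|---|
| Printed | 7.4 | 5% nominal | 61% | 70% | 75% | 90% |
| X ≥ 27 | 6.78 | 11.6% | 71.9% | 80.0% | 84.2% | 95.6% |
| X ≥ 28 | 7.30 | 6.8% | 60.8% | 70.4% | 75.7% | 91.9% |
| X ≥ 29 | 7.89 | 3.6% | 48.7% | 59.0% | 65.0% | 86.1% |

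Of the count rules, only X ≥ 28 is within 2 points of every printed row.

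**What 7.4 implies.** S(5) = 0.5^(5/7.4) = 0.6260, and 0.6260 × 45 = 28.17. Any value that rounds to 7.4 (7.35 to 7.45) maps to 28.08 to 28.26. Twenty-eight alive falls short, so 29 are needed, and power at 7.5 months is 48.7%.

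**7.4 as a cut-off on the observed median.** With complete follow-up this requires at least 23 of 45 alive at 7.4 months. Power is 52.5/64.1/70.7/91.1% and size 2.6%. Simulation with uniform accrual over 24 months plus 6 months' follow-up gives 53/65/72/91% and size 2.8%. The row at 7.5 months remains 8 points or more below 61%.

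**Other scales at N = 45.** Critical medians from normal approximations, before rounding to whole patients:
- log(-log), null variance: 7.12
- linear, Greenwood: 7.23
- linear, null variance: 7.31
- log(-log), Greenwood: 7.51

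None rounds to 7.4. The log(-log) form with null variance for the cut-off and alternative variance for power has cut-off 5 × exp(1.645 × 0.2151) = 7.12. Its power at 7.5 months is Φ[(ln 1.5 − 1.645 × 0.2151)/0.2472] = 58%, and over the four rows 58/68/73/89%. That is within 3 points of each printed row, but with 7.12 and not 7.4.

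**A possible source.** Two per month for 24 months is 48. At N = 48 on the log(-log) scale, the Greenwood critical median is 7.398. Power with null variance for the cut-off and alternative variance for power is 60.4/69.8/75.0/90.5%. Both resemble the printed figures, but they use different variances: the cut-off that goes with that power is 7.04.

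**Why the scale matters.** z against 0.5 at N = 45, critical value 1.645:

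| Alive at 5 months | Linear Greenwood | log(-log) Greenwood |
|---|---|---|
| 27 | 1.37 | 1.28 |
| 28 | 1.69 | 1.55 |
| 29 | 2.02 | 1.81 |

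With 28 alive, the linear scale rejects and the log(-log) scale does not.

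**The case against.** The best defence is that the plan calls the critical value approximate and that the two rules differ by one patient: 7.4 maps to 28.17, and 28 maps to 7.30. Turning a smooth approximation into a hard count of 29 imposes a rule the plan never states. This has some force, but the mismatch does not depend on the count. The observed-median reading and the smooth approximations also fail to give 7.4 months together with 61%.

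A reader might go further and infer that the OS test runs at 6.8% and not 5%, or that the printed power holds only under a rule of inflated size. The documents do not support that. At least 28 of 45 is a rule fitted to the table, and it gives 92% where the plan prints 90%. The plan promises a nominal one-sided 0.05 for a large-sample test, whereas for response in Section 13.6.1 it specifies an exact test. A nominal 5% log(-log) approximation at N = 45 comes within 3 points of every row.

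The 6.8% also assumes nobody is lost before month 5. Section 5.7 lists "Lost to follow-up" as a reason to leave the study, and the study calendar schedules survival contact only every 6 months. If 5% to 10% were lost by month 5 (an assumption), simulated size is 5.6% to 5.7% on the linear scale and 4.0% to 4.2% on the log(-log) scale, both with Greenwood.

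The 48-patient explanation is plausible but remains an inference, since Section 13.6.2 states 45. If it is correct, the printed figures are for the wrong N.

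**Conclusion.** The inconsistency holds at N = 45. With a 7.4-month critical value, power at a true median of 7.5 months is about 49% to 53%, which is 8 to 12 points below the 61% printed. None of the scale and variance choices examined gives both the critical value and the table. This rests on exponential OS, which the plan itself assumes; the count form also needs complete follow-up to month 5.

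The unstated scale is the more practical gap, because the same data with 28 of 45 alive could be called positive or negative. No claim is made that the planned test exceeds its nominal level, since the plan does not define the test closely enough to say.

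The consequence is small. OS is secondary, N comes from PFS, the formal test does not use 7.4, and using 7.4 as a cut-off would be conservative. Correcting the figures would at worst lower the stated power.

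**What to change.** In Section 13.6.2:

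1. Confirm which N produced the critical value and the table.
2. Name one scale for the Brookmeyer-Crowley-type OS test, and say whether Greenwood is its variance as well as that of the bands.
3. Recompute the critical value and all four power figures from that one method at N = 45. State the actual size, and that the count form assumes no loss before month 5.

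For example, log(-log) with Greenwood gives at least 29 of 45 alive at 5 months, a critical value of about 7.9 months, power of about 49/59/65/86% at 7.5/8/8.33/10 months, and exact size 3.6%. If the linear scale with Greenwood is preferred, the rule is at least 28 of 45, about 7.3 months, with power 61/70/76/92%; its exact size of 6.8% should then be stated.

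The cost is text and numbers in one section. Sample size, data collection and analysis timing do not change. Under the log(-log) option, the stated power falls from 61/70/75/90% to about 49/59/65/86%.

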### 13.7 Analysis of Exploratory and Correlative Endpoints

#### Efficacy Endpoints

##### *Intracranial Objective Response:*

There is debate in the field as to the best criteria to use for assessment of response and progression in patients with brain metastases and in patients receiving immunotherapy, and this study provides an opportunity to evaluate efficacy using multiple published criteria in the setting of stereotactic radiation and to compare and contrast these.

All patients who initiate protocol therapy will be evaluated for CNS response according RECIST 1.1, RANO-BM and iRANO-BM criteria.

Lesions treated with stereotactic radiation as part of this protocol will be specifically designated in the case report forms. Based on prior literature, the response rate for stereotactic radiation-treated lesions should be high[Dyer *et al.*, 2012].

In this study, stereotactic radiation-treated lesions can be designated as target lesions, as long as they are reproducibly measurable, and at least 1 cm in longest dimension. It is anticipated that some patients may enter the study with previously treated and stable CNS lesions that are not re-treated as part of the study. These lesions should generally be designated as non-target lesions for the purpose of this study.

Based on a high CNS response rate previously reported with stereotactic radiation alone, we do not necessarily anticipate a detectable increase in the response rate when stereotactic radiation is given in combination with immune checkpoint therapy.

##### *Clinical benefit:*

The proportion of patients with stable or responsive disease in both CNS and non-CNS (each compartment assessed separately; CNS by RANO-BM and non-CNS by RECIST 1.1) at 16 and 24 weeks will be calculated.

##### *Progression free survival*

Historically, PFS has been assessed using RECIST 1.1, which assumes a “single-compartment” summation model. Using RECIST 1.1, up to 2 target lesions may be chosen from each organ site,

with up to 5 total lesions overall. Although the brain can be included as an organ site in RECIST 1.1, frequently, investigators have designated brain metastases as non-target lesions. If brain metastases are instead designated as target lesions, then using RECIST 1.1 as currently written would require that up to 2 lesions in the brain are summed with other target lesions outside of the brain, and progression only deemed when the sum of all longest dimensions exceeds 20% of the sum of nadir on study, and there is an absolute increase of at least 5 mm in at least one lesion.

RANO-BM proposes a bi-compartmental PFS model, such that the CNS and extracranial compartments are evaluated separately, and in this study, bi-compartmental PFS is the primary endpoint. However, there are little to no data comparing the RECIST 1.1 single-compartment model and RANO-BM bi-compartmental model.

In addition, the use of immunotherapy further complicates the assessment of progression. Both irRC and iRANO allow patients to be treated beyond the first demonstration of radiologic progression in order to distinguish between true progression and pseudoprogression. In addition, new lesions do not automatically constitute progressive disease. If true progression is subsequently documented, the date of progression is backdated to the original demonstration of radiographic worsening.

This study will provide a unique opportunity to compare and contrast:

- PFS according to RECIST 1.1, single compartment model, with first progression event deemed an event
- PFS according to RANO-BM, two-compartment model, with first progression event deemed an event
- PFS according to irRC, single compartment model
- PFS according to iRANO, two-compartment model

### Safety and tolerability

All patients will be evaluable for toxicity from the time of their first treatment with any study agent. Toxicity will be graded according to NCI CTCAE, Version 4.0. Toxicities will be summarized by maximum grade.

### Radiation Necrosis

Brain metastases treated with stereotactic radiation which enlarge post treatment will be evaluated for radiation necrosis by the treating radiation oncologist, via neuroradiology assessment, and/or through the use of dual-phase PET-CT studies (Horky *et al.*, 2011), as clinically indicated, according to standard of care. The cumulative incidence of necrosis will be evaluated as the time from first dose of atezolizumab (day 1 cycle 1) to detected necrosis. Patients without detected necrosis will be censored at the end of the study, whether due to death or other reason. Cumulative incidence will be analyzed using Kaplan–Meier product-limit estimates and will be plotted with two-sided 90% confidence bands using Greenwood’s formula for the variance.

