5.2.4.1.8 Stereotactic Radiation Radionecrosis Assessment

To assess participants for potential delayed radiation toxicity, a radiation follow-up visit will be performed approximately 6 months after completion of stereotactic radiation treatment. This visit should be done no earlier than 5 months and no later than 8 months post-stereotactic radiation. Another visit should occur, if possible, around 12 months after completion of radiation treatment. This visit should be performed no earlier than 11 months and no later than 14 months post-radiation. At these timepoints, brain imaging will be correlated with a clinical assessment,

performed by the radiation oncology team. All potential radiation necrosis events will be adjudicated by the PI, [name], in collaboration with the trial radiation oncologist, [name]. A diagnosis of radiation necrosis will be ascribed if:

1. Surgery on an enlarging lesion after radiation reveals a specimen showing predominantly necrosis
  2. Changes consistent with necrosis on dual-phase PETCT are seen
  3. Changes consistent with necrosis on serial MRI studies of the brain are seen.
- Changes consistent with necrosis on serial MRIs of the brain included lack of sustained growth over time in patients who did not receive central nervous system-active systemic therapy after initial enlargement, development of a non-distinct margin of enhancement on T1 post contrast sequences, development of a hypointense center on T1 post contrast images, and a large edema to enhancement ratio.

If a diagnosis of radiation necrosis is made for any patient in this cohort, we will distinguish radiographic necrosis from radiographic and symptomatic necrosis based upon the presence versus absence of associated neurologic symptoms or administration of dexamethasone / bevacizumab for neurologic symptomatology correlating with the anatomic location of the lesion in question.

Every attempt should be made for these assessments to occur in person. Due to the nature of this patient population, some participants may be on hospice or otherwise not able to travel to the study site to complete these endpoints. In these cases, the study team will check to see if any brain imaging has been completed at local facilities and will obtain those images for review. The radiation team may reach out to the patient to perform the radiation necrosis assessment over the phone. Not completing these visits in person will not constitute protocol violations.

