#### 5.5 Criteria for Taking a Participant Off Protocol Therapy

Duration of therapy will depend on individual response, evidence of disease progression and tolerance. In the absence of treatment delays due to adverse event(s), treatment may continue for an indefinite number of cycles, or until one of the following criteria applies:

- Disease progression by iRANO and/or irRC criteria.
  - Please note that although the primary endpoint is bi-compartmental PFS as

defined by standard RANO-BM (for CNS) and RECIST 1.1 (for non-CNS), patients may remain on protocol therapy until the time of disease progression by iRANO and/or irRC criteria. The immune criteria allow treatment beyond initial radiographic worsening of disease in order to distinguish between pseudoprogression and true disease progression.

- Intercurrent illness that prevents further administration of treatment
- Unacceptable adverse event(s)
- Participant demonstrates an inability or unwillingness to comply with the medication regimen and/or documentation requirements
- Participant decides to withdraw from the protocol therapy
- General or specific changes in the participant's condition render the participant unacceptable for further treatment in the judgment of the treating investigator

Participants will be removed from the protocol therapy when any of these criteria apply. The reason for removal from protocol therapy, and the date the participant was removed, must be documented in the case report form (CRF) and in the CTMS system (OnCore). Alternative care options will be discussed with the participant.

In the event of unusual or life-threatening complications, treating investigators must immediately notify the Overall PI, [name] at [REDACTED]

Participants with a documented complete response (CR) may elect to stop Atezolizumab. Subjects who stop atezolizumab with a CR may be eligible for additional atezolizumab therapy if they progress after stopping study treatment. This retreatment is termed the Second Course Phase of this study and is only available if the study remains open and the subject meets the following conditions:

- Stopped initial treatment with atezolizumab after attaining a confirmed and documented CR according to RECIST 1.1, was treated for at least 24 weeks with atezolizumab before discontinuing therapy, and received at least two treatments with atezolizumab beyond the date when the initial CR was declared.

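### Section 13.7 names the cumulative incidence of radiation necrosis but estimates it by Kaplan–Meier with deaths censored, which targets a net risk and not the share of patients affected

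*Combined protocol and SAP*

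**What the plan says.** The Radiation Necrosis paragraph of Section 13.7 starts the clock at the first atezolizumab dose and stops it at detected necrosis. It names the result a cumulative incidence and then says: "Cumulative incidence will be analyzed using Kaplan–Meier product-limit estimates", with two-sided 90% bands from Greenwood's formula. On censoring it says: "Patients without detected necrosis will be censored at the end of the study, whether due to death or other reason".

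Section 5.7 states "Participants will be removed from study when any of the following criteria apply", and death is on the list. For a patient who dies, study participation therefore ends at death. The documents give no competing-risk method and nowhere say that a net risk is intended.

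The provisions for finding necrosis point both ways.

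- **Supporting detection.** Section 5.2.4.1.8 sets radiation visits at about 6 and 12 months, with windows of 5–8 and 11–14 months after radiation. For patients who cannot travel, "the study team will check to see if any brain imaging has been completed at local facilities" and "The radiation team may reach out to the patient to perform the radiation necrosis assessment over the phone". Section 5.5 adds that "patients may remain on protocol therapy until the time of disease progression by iRANO and/or irRC criteria", which can keep some patients on scheduled scanning beyond first progression. Section 5.6 continues CNS follow-up after extracranial progression when the brain is controlled.
- **Limiting detection.** Section 5.2.4.1.8 also says "Not completing these visits in person will not constitute protocol violations", and Section 10, note g, tolerates missed brain scans once therapy has stopped. After intracranial progression, Section 5.6 names survival follow-up only, apart from a phone check for patients who leave therapy before the 6-month radiation visit.

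**The concern.** A curve labelled cumulative incidence will be read as the share of treated patients who developed necrosis by a given time. Censoring deaths removes those patients from the risk set as though they could still develop necrosis later at the same rate as survivors. The label and the estimator therefore refer to different quantities.

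The difference matters in this population because death is frequent on the plan's own survival figures. Safety at 6 and 12 months is a stated exploratory objective (Section 1.4), and this is the only planned time-to-event estimate of necrosis. It will stand beside the symptomatic-necrosis limits of 25% and 50% in Section 13.4, which are on a per-patient scale.

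**Working it through.** The plan states no expected necrosis rate or precision for this analysis, so there is no figure to reproduce. The check sizes the mismatch by illustration.

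**Inputs.** Median overall survival (OS) m is 5 months (null bound) or 10 months (power alternative), from Section 13.6.2, or 7.3 months (historical, from brain-metastasis diagnosis), from Section 2.1. The 1−KM values q of 12.5%, 25% and 50% are the tolerated and unacceptable symptomatic-necrosis rates in Section 13.4. The lower values of 5% and 10% are assumed. None of these is a forecast.

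**Share dead at h months:** 1 − 2^(−h/m).

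| Median OS | Dead by 6 months | Dead by 12 months |
|---|---|---|
| 10 | 34.0% (15.3 of 45) | 56.5% (25.4 of 45) |
| 7.3 | 43.4% (19.5) | 68.0% (30.6) |
| 5 | 56.5% (25.4) | 81.1% (36.5) |

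**Cumulative incidence implied by a given 1−KM**, with constant independent hazards and complete detection:

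- necrosis hazard λn = −ln(1−q)/h
- death hazard λd = ln 2/m
- cumulative incidence = λn/(λn+λd) × (1 − e^(−(λn+λd)h))

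Example with q = 25%, h = 12, m = 5: λn = 0.28768/12 = 0.02397 and λd = 0.69315/5 = 0.13863, which sum to 0.16260. The cumulative incidence is 0.14744 × (1 − e^(−1.9512)) = 0.14744 × 0.85790 = 0.1265, and the ratio is 0.25/0.1265 = 1.98.

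| Horizon, 1−KM | OS 5 (ratio) | OS 7.3 (ratio) | OS 10 (ratio) |
|---|---|---|---|
| 6 mo, 5% | 3.4% (1.47) | 3.8% (1.31) | 4.1% (1.22) |
| 6 mo, 12.5% | 8.6% (1.46) | 9.6% (1.30) | 10.3% (1.22) |
| 6 mo, 25% | 17.3% (1.44) | 19.3% (1.29) | 20.7% (1.21) |
| 12 mo, 10% | 4.9% (2.02) | 6.0% (1.66) | 6.8% (1.46) |
| 12 mo, 25% | 12.6% (1.98) | 15.3% (1.63) | 17.3% (1.44) |
| 12 mo, 50% | 26.6% (1.88) | 31.8% (1.57) | 35.6% (1.41) |

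A simulation with 45 patients, 24 months of uniform accrual and 6 further months of follow-up (4,000 replicates) agrees. With 1−KM at 25% at 12 months, the mean Aalen–Johansen estimates were 12.7%, 15.4% and 17.3% for OS 5, 7.3 and 10.

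**Relaxing complete detection.** Suppose necrosis can be found only before progression, with progression exponential at λp = ln 2/(median PFS) and independent of death. The design medians in Section 13.2 are 2 and 3.5 months. Patients past progression stay in the risk set undetected, so at 12 months:

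- 1−KM as written = λn/(λn+λp) × (1 − e^(−12(λn+λp)))
- Aalen–Johansen with death competing = λn/(λn+λp+λd) × (1 − e^(−12(λn+λp+λd)))

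λn is held at the value that gives a complete-data 12-month 1−KM of 25%. If detection stops at progression in only half of patients, each estimate is the average of its complete-detection and stopped values, for example (25.0 + 10.0)/2 = 17.5.

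| Scenario | True share | 1−KM as written | Aalen–Johansen |
|---|---|---|---|
| OS 10, PFS 3.5, detection stops in all | 17.3% | 10.0% | 8.0% |
| OS 5, PFS 2, detection stops in all | 12.6% | 6.4% | 4.7% |
| OS 10, PFS 3.5, stops in half | 17.3% | 17.5% | 12.6% |
| OS 5, PFS 2, stops in half | 12.6% | 15.7% | 8.7% |

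Stopping in all patients is deliberately extreme, because Sections 5.2.4.1.8, 5.5 and 5.6 provide some later assessment.

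**The case against.** **The censoring date could be the trial's end.** Section 14 defines the end of the study at trial level. If patients who died stayed in the risk set until that date, 1−KM would approximate the cumulative incidence. The paragraph's own reference to death as a reason for censoring, together with Section 5.7, makes this the weaker reading. The ambiguity is still a reason to state the date.

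**Missed necrosis may matter more than the competing risk.** This stands. In every incomplete-detection scenario above, 1−KM is nearer the true share than Aalen–Johansen. A reader might infer from the ratios that the published curve will overstate necrosis by up to twofold. The documents do not support that, because the ratios assume detection that the plan does not secure. It does not rescue the estimator either: agreement that depends on two errors of unknown size cancelling does not make the label right.

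**The analysis is exploratory, and overstating harm is the cautious direction.** The first part is correct and limits the weight of the point. The second holds only with complete detection.

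**Relabelling would be enough.** Calling the curve a net risk would cure the mislabelling, but it would leave the plan with no time-to-event estimate of the share of patients affected.

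**Conclusion.** The estimator does not match the quantity named, and this should be corrected. With complete detection and constant independent hazards, 1−KM exceeds the cumulative incidence by about 1.2–1.5 times at 6 months and 1.4–2.0 times at 12 months, for median OS of 10 down to 5 months. Under complete detection the direction does not depend on the rates chosen. Under incomplete detection the gap from the true share can shrink or change sign, and its net size cannot be determined from the plan.

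Two stronger conclusions are not supported. One is that stopping decisions are compromised: the Section 13.4 boundaries are event counts by number enrolled and do not use this curve. The other is that Aalen–Johansen would by itself recover the true share: it targets the right quantity but inherits any missed necrosis.

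**What to change.** In the Radiation Necrosis paragraph of Section 13.7:

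- Replace Kaplan–Meier and Greenwood with the Aalen–Johansen cumulative incidence, its matching variance and 90% limits, with death without detected necrosis as the competing event. Keep 1−KM only if it is labelled net risk.
- State the censoring date for living patients without necrosis as their last necrosis assessment. For all necrosis, this is the last brain imaging, because the diagnostic criteria in Section 5.2.4.1.8 are surgery, PET-CT or serial MRI and a phone call cannot exclude a radiographic finding. Visit or phone contact counts only for symptomatic necrosis. That section already makes the split: "we will distinguish radiographic necrosis from radiographic and symptomatic necrosis".
- Report estimates at times that include the radiation visit windows. These close 8 and 14 months after radiation, while the clock starts at the first dose, so a 6-month reading can miss events found at the visit labelled 6 months.
- Report how many patients died after necrosis assessment had ceased, and add a sensitivity analysis that censors them at their last assessment. State that the main estimate can understate incidence, and do not present the two estimates as bounds.

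The cost is a short paragraph, standard software, slightly more analysis work, and keeping the date of last necrosis assessment. Sample size and stopping rules do not change.
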